2.4.3 Exploratory Effectiveness Endpoints

2.5 Safety Analysis

Safety endpoints will be summarized using descriptive statistics using the observed cases. There are no planned inferential statistical analyses of safety endpoints.

2.5.1 Treatment Administration, Procedural Anesthetics, and Injection Concomitant Procedures

Treatment administration endpoints that will be summarized by treatment session (Group A only) include (but are not limited to):

- Injection volume
- Injection method
- Depth of injection.

The number of subjects with any procedural anesthetics will be summarized by type and location.

The number of subjects with any injection concomitant procedures will be summarized.

2.5.2 Pre-Defined Expected Post-Treatment Symptoms (Subject Diary, Group A only)

Number and percentage of subjects reporting each pre-defined, expected, post-treatment symptoms, as collected in the 28-day diary, will be presented in total and by maximum intensity. Number of days with the event will be presented by category: 1, 2-7, 8-14, and 15-28 days.

2.5.3 Adverse Events (AEs)

All AEs will be coded according to MedDRA and summarized by system organ class (SOC) and preferred term (PT) for each treatment group.

Typically, only AEs that occur during the extension period will be summarized. A summary of all related AEs that includes those occurring from the pivotal study to end of the extension study will be provided for Group B only.

AEs related to study product or injection procedure and unrelated AEs will be presented by maximum intensity, SOC and PT. For related AEs, the number of days to onset and the duration of event will be summarized by SOC and PT using mean, SD, min, max and median. Action taken for related AEs will also be summarized by SOC and PT. Serious AEs will be listed.

In addition, a summary of all AEs will be provided, which will include (but is not limited to):

- number of subjects with at least one AE and number of events (in total as well as serious AEs)
- number of subjects with at least one related AE and number of events (in total as well as serious AEs)
- number of subjects with at least one un-related AE and number of events (in total as well as serious AEs)
- number of subjects who did not have an AE

Adverse events will also be summarized by the following subgroups:

- Study Center
- Age Group (<55 years vs. \geq 55 years)
- FST Skin Type
- Injection Technique (including techniques of Bolus, Fanning, Cross Hatching, Linear Antegrade, etc. and all observed combinations of these [e.g. Bolus * Fanning, Bolus * Linear Retrograde, Cross Hatching * Fanning * Linear Retrograde, etc.]).
- Pre-Treatment CCI

Adverse events of special interest (all incidences of visual disturbances, regardless of relationship to study product or seriousness) will be summarized. Adverse events related to study product or injection procedure will be summarized by session.

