8.6.10 Follow-up of unresolved events ongoing at termination of the study

All serious as well as non-serious AEs with a causal relationship to the study product or treatment procedure and ongoing at study end, shall be followed up after the subject's participation in the study is over. Such events shall be followed-up after the last study visit until resolved, assessed as chronic or stable, or subject is lost to follow up. Follow-up information shall be reported on the AE follow-up form.

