10.5 Safety analysis

Number and percentage of subjects reporting each pre-defined, expected, post-treatment symptoms, as collected in the 28-day diary, will be presented in total and by maximum intensity. Number of days with the event will be presented by treatment group and category: 1, 2-7, 8-14, and 15-28 days.

All AEs will be coded according to MedDRA and summarized by system organ class (SOC), preferred term (PT) and treatment.

AEs related to study product or injection procedure and unrelated AEs will be presented by maximum intensity, SOC and PT. For related AEs, the number of days to onset and the duration of event will be summarized by SOC and PT using mean, SD, min, max and median. Action taken for related AEs will also be summarized by SOC and PT. Serious AEs will be listed.

In addition, a summary of all AEs will be provided, which will include (but is not limited to):

- number of subjects with at least one AE and number of events (in total as well as serious AEs)

- number of subjects with at least one related AE and number of events (in total as well as serious AEs)
- number of subjects with at least one un-related AE and number of events (in total as well as serious AEs)
- number of subjects who did not have an AE

Functionality, sensation, firmness, symmetry, mass formation and palpation assessments will be analyzed descriptively as appropriate.

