2.1.4 Handling of Missing Data

Number of missing values will be summarized and reported as appropriate.

All effectiveness endpoints will be evaluated based on the observed cases.

Descriptive statistics of all safety data will be performed on observed cases.

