2.5.4 Other Safety Analyses

Visual function will be summarized by visit, along with each visit's change from pre-treatment (Group A only), and 95% confidence intervals, via t-distribution, will be provided for the change.

Functionality, sensation, firmness, symmetry, mass formation, palpation assessments, and device deficiencies will be analyzed descriptively as appropriate.

The incidence of nodules, papules, and granuloma (defined as AEs with system organ class containing "nodule", "papule", or "granuloma") will be summarized, including the time to onset from the pre-treatment visit as well as the duration.

[figure not shown]
Weight and BMI will additionally be summarized at each visit along with change from the pre-treatment visit.

Effective date: 2022-03-08 18:10

Effective

Version: 2.0

2022-03-08 18:10

Effective date:

Effective

Version: 2.0

[figure not shown]
Statistical Analysis Plt

CCI

GALDERMA
EST. 1981

4 Rasch Transformation of FACE-Q

CCI

Statistical Analysis Fl

CCI
GALDERMA
EST.1981

5 Schedule of Events (Treatment and Control Groups)

Table 1. Schedule of events, **Group A** (subjects receiving Treatment in 43USSA1812ext)

	Visit 5 ¹ Final Study Visit 43USSA1812	Visit 1 ² Extension Study Entry Treatment 1	Visit 1a: Telephone Contact	Visit 2: Month 13 Treatment 2 ⁴ (Optional)	Visit 2a: Telephone Contact ⁷	Visit 3: Month 14 Treatment 3 ⁸ (Optional)	Visit 3a: Telephone Contact ⁷	Visit 4: Month 15 Treatment 4 ⁹ (Optional)	Visit 4a: Telephone Contact ⁷	Visit 5: Month 19 Follow-up	Visit 6: Month 21 Follow-up	Visit 7: Month 24 Final visit/ Early termination
	Month 12 (± 2 weeks) after Baseline	(± 2 weeks) after Visit 5	72 hours (± 24 hrs) after Treatment 1	1 month (± 2 weeks) after Treatment 1	72 hours (± 24 hrs) after Treatment 2	1 month (± 2 weeks) after Treatment 2	72 hours (± 24 hrs) after Treatment 3	1 month (± 2 weeks) after Treatment 3	72 hours (± 24 hrs) after Treatment 4	7 months (± 2 weeks) after ext. Visit 1	9 months (± 2 weeks) after ext. Visit 1	12 months (± 2 weeks) after ext. Visit 1
Informed consent		X										
Inclusion/Exclusion criteria		X ⁴		X ⁴		X ⁴		X ⁴				
Demographics incl. weight	X	X ³								X ³	X ³	X ³
Concomitant therapies	X	X	X	X	X	X	X	X	X	X	X	X
Urine pregnancy test ^{4,5}	X			X		X		X				
Photography (2D and 3D)	X	X ⁴		X ⁴		X ⁴		X ⁴		X	X	X
Sculptra Aesthetic administration		X		X ⁶		X ⁶		X ⁶				
Adverse event assessment	X	X	X	X	X	X	X	X	X	X	X	X
Safety Assessments ¹¹	X	X		X		X		X		X	X	X

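### The plan has no visible rule for the duration of unresolved related adverse events, so reported persistence of long-lasting events such as nodules would be too short

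*SAP*

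**What the plan says.** Adverse event duration is a named safety endpoint (protocol 3.2, SAP 1.6). For related events, SAP 2.5.3 says that "the duration of event will be summarized by SOC and PT using mean, SD, min, max and median". Protocol 10.5 gives the same list: "the number of days to onset and the duration of event will be summarized by SOC and PT using mean, SD, min, max and median".

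For nodules, papules and granuloma, SAP 2.5.4 promises an incidence summary "including the time to onset from the pre-treatment visit as well as the duration". It names no statistic for that duration.

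On missing data, SAP 2.1.4 says "Descriptive statistics of all safety data will be performed on observed cases", as does protocol 10.6. SAP 2.1.4 adds "Number of missing values will be summarized and reported as appropriate".

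Protocol 8.6.10 covers related events still open at the end of the study: "Such events shall be followed-up after the last study visit until resolved, assessed as chronic or stable, or subject is lost to follow up". It then says where the result goes: "Follow-up information shall be reported on the AE follow-up form".

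The only time-to-event method in the visible SAP is Kaplan-Meier for return to social engagement (SAP 2.4.2).

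**The concern.** Mean, SD, minimum, maximum and median all need a completed duration for every event. An event without a resolution date does not supply one. If it is dropped, the summary describes only the events that ended. If it is cut at the last contact, it enters with a value below its true length. Neither choice can lengthen the reported persistence, and both act mainly on the longest events.

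This matters because the extension was set up to describe the long-term safety of the more dilute suspension (protocol 2.3). Protocol 2.4 names late-onset papules, nodules and granuloma as something the study should inform. It also expects most, and so not all, of these lesions to resolve. Some unresolved events must therefore be expected, and for those events the length of persistence is what a reader needs to know.

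**Working it through.** The documents give no duration figure to reproduce, so the check has two parts: what the text provides for an unresolved event, and how large the effect could be.

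**Text.** Protocol 8.6.10 has three end states: resolved, chronic or stable, and lost. Only the first gives a natural stop date. Routine reporting runs to the last scheduled visit (protocol 8.6.5), and analyses use the locked datasets (protocol 9.1). No visible text says that dates from the AE follow-up form enter those datasets, or up to when. For events ongoing at withdrawal, protocol 5.5 points to 8.6.11, which deals with onset after the last visit.

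**Size, inputs.**
- From the documents: extension follow-up of 12 months × 28 days = 336 days (protocol 4.1: one month is 4 weeks), ignoring windows.
- Assumed: exponential durations with true median M, so λ = ln 2 / M; onset uniform over days 0–336, or over days 0–112; a share f of the events unresolved at day 336 never receives an end date and is dropped; the rest are followed to resolution.

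**Formula, onset over days 0–336.** An event of length t < 336 is unresolved at day 336 with probability t/336. The overall unresolved share is U = (1 − e^(−336λ)) / (336λ). The reported median m solves

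∫₀ᵐ λe^(−λt)(1 − f·t/336) dt = ½(1 − fU), for m < 336.

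**M = 180.** λ = 0.003851 and 336λ = 1.294, so U = (1 − 0.274)/1.294 = 0.561.
- f = 0.25: the right side is ½(1 − 0.140) = 0.430. At m = 157 the left side is 0.454 − 0.25 × 0.095 = 0.430. The reported median is about 157 days.
- f = 1: the right side is ½(1 − 0.561) = 0.2195. At m = 72.9 the left side is 0.245 − 0.025 = 0.2195, before rounding of its terms. The reported median is about 73 days.

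A simulation of 400,000 events per scenario gave 157.2 and 72.8 days, and the following medians:

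| True median (days) | Onset (days) | Unresolved at day 336 | f = 0.25 | f = 0.50 | f = 1 |
|---|---|---|---|---|---|
| 30 | 0–336 | 12.9% | 29.0 | 28.0 | 26.0 |
| 90 | 0–336 | 35.7% | 82.1 | 73.6 | 55.6 |
| 180 | 0–336 | 56.2% | 157.2 | 130.4 | 72.8 |
| 365 | 0–336 | 73.9% | 320.5 | 252.5 | 84.9 |
| 30 | 0–112 | 0.2% | 30.0 | 30.0 | 29.9 |
| 90 | 0–112 | 12.0% | 86.0 | 82.3 | 75.2 |
| 180 | 0–112 | 34.2% | 158.7 | 139.2 | 103.5 |
| 365 | 0–112 | 59.0% | 300.8 | 230.9 | 121.6 |

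With f = 0 (every date recovered) there is no bias. For a true median of 14 days the shortfall is at most about 1 day.

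**Cutting at day 336 instead of dropping.** For M = 180 and onset over days 0–336, the median is 94.3 days and the mean 113.9, against a true mean of about 260. With onset over days 0–112 the median is unbiased (180.1), but the mean is 170.6 against 259.

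**Kaplan-Meier with censoring at day 336.** It recovers 30, about 90 and about 180 days. For a true median of 365 days the median is not reached.

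**The case against.** The strongest reply is that the SAP is silent, not wrong. The observed-case rule does not say whether an ongoing event is dropped, cut, or shown as ongoing. Table formats are in a companion document (SAP 2.1.2), where an ongoing row could appear. Part of protocol 8.6.4 on recording, and the material between SAP 2.5.4 and SAP section 4, are not in the text available for review. This stands. A reader might infer that the plan excludes unresolved events by rule, or that its durations are certain to be biased. The documents do not support either statement.

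Protocol 8.6.10 also does real work. It covers the same related events that SAP 2.5.3 summarises, and it removes the bias for those that later resolve, provided the dates reach the analysis. It does not help where the event is closed as chronic, stable or lost.

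The largest figures are near the worst case. Injections fall nominally at extension days 0, 28, 56 and 84, or at most about day 126 with three intervals of 28 + 14 days, so many onsets will be early. For Group B, the combined summary of related events starts in the pivotal study, so 336 days is not its follow-up.

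Unresolved events do not vanish from the report: they count in the incidence tables and appear in the listings (SAP 2.1.2, 2.5.3). Nor can a mean or median duration confirm or refute the background remark that most lesions resolve, because that remark is about a proportion.

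Finally, with about 50 subjects treated in the extension and a purely descriptive safety analysis, Kaplan-Meier for every SOC and PT cell would be impractical. This is accepted, and the request is limited accordingly.

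**Conclusion.** The point holds in a conditional form. The stated statistics cannot represent an event without an end date, no visible text supplies a rule, and any distortion from omission or truncation is towards shorter persistence. It falls on the longest-lasting events. Protocol 8.6.10 reduces the problem but does not close it.

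The size depends on the share of events never given an end date. It is negligible for short events. For an assumed true median of 180 days and onset uniform over days 0–336, the reported median would be about 157 days if 25% of the events unresolved at day 336 stay undated, and about 73 days if all do. These figures rest on assumed exponential durations and assumed onset times. They are not a forecast for this trial, and it would be wrong to read 73 days as the expected result. The SAP should be changed, because duration is a named endpoint and the remedy is cheap.

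**What to change.** In SAP 2.5.3 and 2.5.4:

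1. Beside every duration summary, show the number and percentage of events ongoing, closed as chronic or stable, and lost. Label the mean and median as applying to resolved events only.
2. State that end dates from protocol 8.6.10 follow-up are included, up to a named cut-off.
3. For nodules, papules and granuloma as one pooled group, estimate duration by Kaplan-Meier with unresolved events censored at last contact. Report the median as not reached where that is the case. Other terms with enough events may be treated the same way.

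The cost is a few lines of SAP text, extra table columns and a short program, using a method the SAP already applies to return to social engagement. Before database lock this is a SAP amendment; after it, the change is documented in the study report (SAP 2.1). The downside is that reported durations become longer or cannot be estimated. Repeated events within a subject are also treated as independent unless this is handled, for example by counting each subject's first event or by using a subject-level variance.

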2.5.4 Other Safety Analyses

Visual function will be summarized by visit, along with each visit's change from pre-treatment (Group A only), and 95% confidence intervals, via t-distribution, will be provided for the change.

Functionality, sensation, firmness, symmetry, mass formation, palpation assessments, and device deficiencies will be analyzed descriptively as appropriate.

The incidence of nodules, papules, and granuloma (defined as AEs with system organ class containing "nodule", "papule", or "granuloma") will be summarized, including the time to onset from the pre-treatment visit as well as the duration.

[figure not shown]
Weight and BMI will additionally be summarized at each visit along with change from the pre-treatment visit.

Effective date: 2022-03-08 18:10

Effective

Version: 2.0

2022-03-08 18:10

Effective date:

Effective

Version: 2.0

[figure not shown]
Statistical Analysis Plt

CCI

GALDERMA
EST. 1981

4 Rasch Transformation of FACE-Q

CCI

Statistical Analysis Fl

CCI
GALDERMA
EST.1981

5 Schedule of Events (Treatment and Control Groups)

Table 1. Schedule of events, **Group A** (subjects receiving Treatment in 43USSA1812ext)

	Visit 5 ¹ Final Study Visit 43USSA1812	Visit 1 ² Extension Study Entry Treatment 1	Visit 1a: Telephone Contact	Visit 2: Month 13 Treatment 2 ⁴ (Optional)	Visit 2a: Telephone Contact ⁷	Visit 3: Month 14 Treatment 3 ⁸ (Optional)	Visit 3a: Telephone Contact ⁷	Visit 4: Month 15 Treatment 4 ⁹ (Optional)	Visit 4a: Telephone Contact ⁷	Visit 5: Month 19 Follow-up	Visit 6: Month 21 Follow-up	Visit 7: Month 24 Final visit/ Early termination
	Month 12 (± 2 weeks) after Baseline	(± 2 weeks) after Visit 5	72 hours (± 24 hrs) after Treatment 1	1 month (± 2 weeks) after Treatment 1	72 hours (± 24 hrs) after Treatment 2	1 month (± 2 weeks) after Treatment 2	72 hours (± 24 hrs) after Treatment 3	1 month (± 2 weeks) after Treatment 3	72 hours (± 24 hrs) after Treatment 4	7 months (± 2 weeks) after ext. Visit 1	9 months (± 2 weeks) after ext. Visit 1	12 months (± 2 weeks) after ext. Visit 1
Informed consent		X										
Inclusion/Exclusion criteria		X ⁴		X ⁴		X ⁴		X ⁴				
Demographics incl. weight	X	X ³								X ³	X ³	X ³
Concomitant therapies	X	X	X	X	X	X	X	X	X	X	X	X
Urine pregnancy test ^{4,5}	X			X		X		X				
Photography (2D and 3D)	X	X ⁴		X ⁴		X ⁴		X ⁴		X	X	X
Sculptra Aesthetic administration		X		X ⁶		X ⁶		X ⁶				
Adverse event assessment	X	X	X	X	X	X	X	X	X	X	X	X
Safety Assessments ¹¹	X	X		X		X		X		X	X	X

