8.4 Visual Function assessments

Visual function assessments will only be performed for subjects receiving treatment in the extension study (Group A). These assessments will be performed both prior to and post injection of the study product at all treatment visits and will also be performed at each follow up visits. The post-treatment

assessments should be performed 30 min after the injections are completed. In the event of blindness or any significant ophthalmic sign or symptom, subjects are to undergo immediate evaluation by an ophthalmologist or a retina specialist. All incidences of visual disturbances, regardless of relationship to study product or seriousness, are considered Adverse Events of Special Interest (AESIs) and include but are not limited to the following: any loss of vision, blurry vision, double vision, pain in or around the eye, blind spot or shadow in the visual field, trouble moving eyes. AESI's should be reported (using the Adverse Event Clarification Form) within 24 hours of awareness. Please refer to recording instructions in [Section 8.6.6](#).

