8.4.1 Snellen visual acuity test

A Snellen Eye Chart will be used to assess visual acuity for distance vision. Visual Acuity will be conducted using the subject's best distance correction (e.g. with contacts or spectacles) at a distance of 6 feet from the chart. Each eye will be measured separately by either using an occluder or having the subject cover one eye at a time. The subject will be asked to start reading the letters at the top of the chart working their way to the bottom. The smallest row of letters that the subject can read will indicate their visual acuity listed on the chart. Snellen Visual Acuity will be recorded in their source documentation and eCRF. If there are two or more visual acuity line changes during the course of study, these should be reviewed and assessed by the Investigator for a potential adverse event.

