1.3 Effectiveness Assessments

For all assessments, the baseline visit (hereafter referred to as the “pre-treatment visit”) will be defined as the observation that is closest to but prior to study treatment. In other words, the pre-treatment visit for Group A will occur after the pivotal study, but before treatment in the extension study (e.g. Month 12 pre-treatment). For Group B, the pre-treatment visit will be the same as what was used in the pivotal study (e.g. Day 1).

Change from pre-treatment will be calculated for each group as the value at a given time point minus the pre-treatment value. Note that the first visit in the extension study, the Study Entry Visit, is equivalent to the pre-treatment visit for Group A, but this is not true for Group B.

Effective date: 2022-03-08 18:10

Effective date: 2022-03-08 18:10

Effective

Version: 2.0

CCI

CCI

The severity of cheek wrinkles will be assessed live by the Blinded Evaluator using the validated 5-graded GCWS [REDACTED] during the study. The GCWS [REDACTED] scale is a validated photograph-based outcome instrument.

CCI

The severity of cheek wrinkles will be assessed live by the Blinded Evaluator using the validated 5-graded GCWS [REDACTED] during the study. The GCWS [REDACTED] scale is a validated photograph-based outcome instrument.

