2.1.2 Reporting Conventions

The formats for the tables, listings, and figures described in this SAP will be provided in a companion document. Changes to the formats of these reports that are decided after the finalization of the SAP will not require an amendment. In addition, any additional supportive **CCI** analyses requested after SAP approval will not require amendment of the SAP. These additional analyses will be described in the CSR.

All study data from the eCRFs as well as derived variables will be provided in subject data listings. An indication of specific listings for each data type will not be indicated in the text of subsequent SAP sections. Data listings supplied as part of the CSR will be sorted by study center number concatenated with subject number, assessment dates, and/or time point.

The following conventions will be applied to all data presentations and analyses:

- Quantitative variables will generally be summarized by the number of subjects, mean, standard deviation (SD), median, minimum (min), and maximum (max). Unless otherwise specified, the minimum and maximum values will be displayed to the same number of decimal places as the raw data, the mean and median will be presented to one extra decimal place compared to the raw data, and the standard deviation will be displayed to two extra decimal places compared to the raw data
- Categorical variables will be summarized by the number and percentage of subjects (and number of events where appropriate) within each category. Unless otherwise specified, the percentage will be presented in parentheses to one decimal place. Frequency and percentage values of 0 will be presented as '0 (0)'.
- All summary tables will include the analysis population sample size (i.e. number of subjects).
- Date variables will be formatted as DDMMYY for presentation.
- Confidence intervals will be two-sided and constructed at the 95% confidence level.

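### Visual function is planned only as change from the Month 12 entry visit with a t-interval: no same-day injection change at Visits 2 to 4, no two-line count, and a poor fit for two binary tests

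*SAP*

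**What the plan says.** Visual function assessments are a safety endpoint of their own, listed apart from adverse events, for Group A only (Protocol 3.2, SAP 1.6). There are three tests: Snellen acuity, extraocular muscle function and confrontation visual field.

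- **Collection.** Protocol 8.4: "These assessments will be performed both prior to and post injection of the study product at all treatment visits". On the second reading, the "assessments should be performed 30 min after the injections are completed". Follow-up visits are tested as well.
- **Scale.** Snellen acuity is measured for each eye separately (Protocol 8.4.1). The other two tests are recorded as normal or abnormal (Protocol 8.4.2 and 8.4.3).
- **Trigger.** Protocol 8.4.1: "If there are two or more visual acuity line changes during the course of study", the investigator is to review them as a potential adverse event. No direction and no reference time point are given.
- **Analysis.** SAP 2.5.4: "Visual function will be summarized by visit, along with each visit's change from pre-treatment (Group A only". The change is to be given with t-based intervals at the 95% level. No other SAP sentence analyses this endpoint, and Protocol 10.5 does not name it.
- **Reference.** SAP 1.3, in a definition said to hold for all assessments: "the pre-treatment visit for Group A will occur after the pivotal study, but before treatment in the extension study (e.g. Month 12 pre-treatment". It adds that "the first visit in the extension study, the Study Entry Visit, is equivalent to the pre-treatment visit for Group A".

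**The concern.** Protocol 2.4 introduces the visual tests because of rare but serious vision impairment after intravascular injection, and Protocol 8.6.8 includes vision loss in the stopping rule. The pair of readings around each injection is the part of the design that isolates an acute effect of that injection.

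The planned analysis does not use that pair after Visit 1. At Visits 2 to 4 it refers back to the entry visit, so a same-day change is mixed with whatever has happened since. A t-interval then describes the average subject, whereas a rare acute event shows in individuals. For the two normal/abnormal tests, a t-interval on change does not suit the data at all. The report could therefore contain the readings and still not show how many eyes or subjects worsened between the needle and the 30-minute test.

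**Working it through.** The plan states no figure on this point, so there is none to reproduce. The check traces the reference and then illustrates how the planned summary behaves.

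**1. Age of the reference.** Protocol 6.5.2 allows up to four sessions at one-month intervals with a window of +2 weeks; a month is 28 days. Session k is then (k - 1) × 28 days after entry nominally and (k - 1) × 42 days at the latest.

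| Session | Nominal | Latest |
|---|---|---|
| 2 | 28 days | 42 days |
| 3 | 56 days | 84 days |
| 4 | 84 days | 126 days |

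**2. What the planned change contains.** Let R be the entry reading, and pre and post the two readings at one session. Then

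post - R = (post - pre) + (pre - R).

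- Visit 1: R is the pre-injection reading, so post - R is the same-day change, provided the 30-minute record represents the visit. If the pre-injection record does, the change is zero by definition. The SAP does not say which record is used.
- Visits 2 to 4: the second term enters. Example: an eye one line above R before injection and one line below R afterwards has lost two lines that day. Its planned change is -1, or +1 if the pre-injection record is used.

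**3. Mean against count.** Assumptions: n = 50 (the approximate size of Group A), one value per subject, change scored in lines, all other subjects unchanged. If k subjects lose L lines, the mean is -kL/n and the interval is mean ± t(0.975, 49) × SD/√50. The exact interval for k/n is Clopper-Pearson.

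| Loss | Mean change (95% t CI) | Count (exact 95% CI) |
|---|---|---|
| 1 subject, 2 lines | -0.04 (-0.12 to 0.04) | 2.0% (0.05% to 10.65%) |
| 1 subject, 5 lines | -0.10 (-0.30 to 0.10) | 2.0% (0.05% to 10.65%) |
| 3 subjects, 2 lines | -0.12 (-0.26 to 0.02) | 6.0% (1.25% to 16.55%) |
| 5 subjects, 2 lines | -0.20 (-0.37 to -0.03) | 10.0% (3.33% to 21.81%) |

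Background variation widens the t-interval. With an assumed SD of change of 0.5 to 1.0 line (not in the documents), the half-width is 0.14 to 0.28 line, against a shift of 2/50 = 0.04 from one two-line loss.

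**4. The two binary tests.** An abnormal result on either test excludes a subject from treatment (Protocol 5.3, criterion 18), and eligibility is confirmed again before each session. If this is followed, every treated subject is Normal beforehand. For these tests the choice of reference then matters little; the form of the summary matters. Code Abnormal as 1:

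- 0 of 50 abnormal: SD = 0, so the t-interval is 0 to 0. The exact upper limit is 1 - 0.025^(1/50) = 7.1%.
- 1 of 50 abnormal: mean 0.02, SD = √(0.98/49) = 0.141, SE = 0.02, t-interval about -0.02 to 0.06. A negative change is impossible when all start Normal. The exact interval is 0.05% to 10.65%.

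**The case against.** The strongest reply has four parts.

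**Other outputs cover the serious cases.** SAP 2.5.3 summarises all visual disturbances as events of special interest and related events by session. SAP 2.1.2 lists all eCRF data, and its default summary gives the minimum and maximum as well as the mean. A reader might infer that a large loss would be hidden; the documents do not support that, since a five-line loss would probably appear as an extreme value. This stands. But the minimum and maximum are still measured from Month 12, the event tables depend on investigator judgement, and listings give no count or denominator.

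**The same-day change is not wholly lost.** A reader might infer that it is never analysed. Visit 1 can supply it, so that reading is too strong. Sessions 2 to 4 are also optional, so four pairs per subject is a maximum.

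**The two-line figure is not an endpoint.** A reader might take it as a protocol threshold that the SAP fails to analyse. Protocol 8.4.1 makes it only a prompt for review, with no tie to the 30-minute test. A same-day count at two lines borrows that figure as a convenient cut-off.

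**The reference may be per session.** The schedule footnotes mark visual testing as pre-treatment at each treatment visit, and SAP 2.5.4 says pre-treatment here but the pre-treatment visit for weight. That reading is possible. It conflicts with the single definition in SAP 1.3, although that sits in the effectiveness section, and it gives no reference for the follow-up visits. Table layouts are in a companion document not available here, so separate pre-injection and 30-minute rows cannot be excluded.

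**Conclusion.** The point holds as a defect of summary, not of data collection. On the natural reading of SAP 1.3 with 2.5.4, no within-visit change is defined for Visits 2 to 4, which is up to three of the four possible sessions. No table counts Snellen changes of two or more lines, and a t-interval is specified for two tests that have only two outcomes. Such changes reach the report through extremes measured against Month 12, listings, or events that an investigator chose to record.

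The size is modest in this descriptive extension. In the illustration, up to three two-line losses among 50 subjects leave the t-interval including zero, while a count would show 6.0%. That rests on about 50 subjects, one value per subject, acuity scored in lines and no other variation. How far acuity drifts between entry and later sessions is not known from the documents. Nothing here suggests that a visual event would go unreported; the weakness is that the listed endpoint would not itself show the change around each injection.

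**What to change.** In SAP 2.5.4:

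1. For each injection session actually given, report the number and percentage of eyes with a Snellen worsening of two or more lines from the same-day pre-injection reading to the 30-minute reading. State that the cut-off is taken from the investigator-review trigger and is descriptive.
2. Over the same interval, report Normal-to-Abnormal shift counts by subject for the extraocular muscle and confrontation field tests.
3. Give the same counts from the extension pre-treatment visit to Months 19, 21 and 24.
4. Use shift counts in place of t-intervals for the two binary tests.
5. Keep the Snellen change from pre-treatment as supportive, and say whether the pre-injection or the 30-minute record represents each treatment visit.

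If an interval is wanted for the Snellen count, base it on subjects with at least one such eye, because two eyes of one subject are not independent.

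The cost is one additional safety table from readings already collected. No procedure, review trigger or clinical rule changes. Because the text of 2.5.4 changes, SAP 2.1 calls for an amendment if this is done before database lock; later, it belongs in the study report.
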